### 5.1.3. Immunogenicity Visit Windows

For the immunogenicity analysis, assessments will be allocated to an analysis visit based on the planned visit as captured in the CRF. Visits that are out of the protocol-defined visit windows (see table below) will not be included in the per-protocol immunogenicity analysis. However, they may be included in sensitivity analyses.

**Table 5: Immunogenicity timepoints**

Analysis timepoint	Reference day	Target day (counted from the reference day)	Window
Baseline	Day of vaccination 1	1	$(-\infty, 1]$
Day 15	Day of vaccination 1	15	[12, 18]

### 5.2. Participant Dispositions

Participant information will be shown for the full analysis set.

The number of participants in the following disposition categories will be summarized throughout the study by intervention group and overall:

- participants screened
- participants in the FAS
- participants not randomized and not vaccinated
- participants not randomized and vaccinated
- participants randomized and not vaccinated
- participants randomized and vaccinated
- participants who discontinued study
- reasons for termination

Also, the number of participants and percentage per phase will be tabulated.

Other participant information variables: demographics and baseline characteristics, major protocol deviations, and concomitant medications will be analyzed as described in [Appendix 3](#), [Appendix 4](#) and [Appendix 5](#), respectively. Medical history and concomitant diseases will be tabulated.

## **5.3. Primary Endpoint(s) Analysis**

### **5.3.1. Definition of Endpoint(s)**

The primary endpoint is the pre-F enzyme-linked immunosorbent assay (ELISA) antibody titer at 14 days after vaccination.

### **5.3.2. Analysis Methods**

The primary immunogenicity objective will be assessed by calculating the 2-sided 95% CIs for the difference in log-transformed Day 15 pre-F ELISA titers (ie, Group 1 versus Group 2).

The CI will be calculated via an analysis of variance (ANOVA) including both groups with Day 15 pre-F ELISA titers as dependent variable and group as independent variable. The CIs around the difference will be back-transformed (by exponentiation) to CIs around a GMR (GMTPhase 3 CTM/GMTPhase 2b CTM) and compared to the non-inferiority limits of 0.67 (2/3).

Non-inferiority between the Phase 3 CTM versus the Phase 2b CTM is demonstrated if the lower limit of the 2-sided 95% CI of the estimated GMR lies entirely above 0.67.

As a sensitivity analysis to assess the impact of baseline titers, the primary endpoint will also be evaluated adjusting for the respective baseline titers. For immunogenicity, baseline is considered as the last assessment pre-vaccination. In a second sensitivity analysis, different variances between the groups will be allowed. Therefore, the CIs will be calculated via Welch's ANOVA.

The significance level ( $\alpha$ ) is 5% (2-sided). As no interim analyses before the primary analysis are planned, no multiplicity adjustments are needed.

Pre-F ELISA titers will be summarized with descriptive statistics. Descriptive statistics (N, geometric mean§ and corresponding 95% CI) of the actual values will be calculated for continuous immunogenicity parameters at all timepoints. Geometric mean§ fold increases from baseline and corresponding 95% CIs might additionally be calculated. *§calculate the mean and corresponding 95%CI of the log2 transformed values, back-transform this mean [ie 2mean] and CI [ie 2CI].*

The tables will also show the fold increases together with the percentage of participants with a 2- and a 4 -fold increase from baseline.

Actual values and fold changes from baseline will also be presented in dot-plots with dots for participant values, and the corresponding geometric mean and 95% CI per timepoint. In addition, plots of GMT over time, combining the regimens in one graph (without individual participant dots) will be created. Reverse distribution curves of the actual values will be provided, for baseline and Day 15. In the graphs, original values will be displayed on the log2 scale.

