**Table 2: Study Design**

Group	N	
1	120	Phase 3 CTM a
2	120	Phase 2b CTM b

CTM clinical trial material; N number of participants

a representative of future commercial manufacturing process material (Ad26.RSV.preF Lot 2 + RSV preF protein Lot b)

b representative of Phase 2b (VAC18193RSV2001) CTM (Ad26.RSV.preF Lot 4 + RSV preF protein Lot d)

After vaccination, participants will remain under observation at the study site for at least 15 minutes for presence of any acute reactions and solicited events. Any unsolicited AEs, solicited local (injection site) or systemic AEs, and vital signs (systolic and diastolic blood pressure [sitting], heart rate, respiratory rate, and body temperature) will be documented by study-site personnel following this observation period. In addition, participants will record solicited signs and symptoms in a participant diary beginning on the evening of the day of vaccination and on a daily basis for 7 days post-vaccination ([Section 8](#)).

The reporting periods of AEs, SAEs, and AESIs are detailed in [Section 8.3](#). Reporting periods for concomitant therapy are outlined in [Section 6.8](#).

Blood will be collected from all participants to assess humoral immune responses pre-vaccination, at 14 days post-vaccination.

Safety issues that might arise from this study may be escalated to an independent DMC, as needed.

The study duration will be approximately 6 months per participant. The study comprises screening and vaccination for each participant on Day 1, a 28-day safety follow-up period after vaccination, and collection of SAEs and AESIs until 6 months after vaccination. The end of the study is defined as the last participant's last visit.

Over the entire study, the total blood volume to be collected from each participant will be approximately 20 mL.

Unscheduled study visits may be performed based on investigator's clinical judgment and may include further evaluations, as needed.

A diagram of the study design is provided in [Section 1.2](#) ([Figure 1](#)). Further details are provided in the [Schedule of Activities](#).

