#### **9.2. Sample Size Determination**

Sample size calculations were performed under the following assumptions:

- no difference in the Day 15 pre-F ELISA between the Phase 3 CTM and the Phase 2b CTM (ie, assuming a true GMR of Day 15 pre-F ELISA titers equal to 1)
- a standard deviation of 1.3 at the  $\log_2$  scale for pre-F ELISA on Day 15a
- a non-inferiority margin of 0.67 (2/3)
- 2-sided  $\alpha$  of 5%

A total of 105 evaluable participants per group are needed to have 90% power to demonstrate non-inferiority.

---

a Based on Day 15 pre-F ELISA results obtained from Cohort 2, Group 14 in study VAC18193RSV1004.

To account for exclusions from the Per-protocol Immunogenicity (PPI) Set (see Section 9.3), drop-outs and missing samples, approximately 120 participants per group should be enrolled.

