## 5. STATISTICAL ANALYSES

### 5.1. General Considerations

#### 5.1.1. Study Phases

A baseline (or reference) value will be defined as the value of the last available assessment prior to vaccination on Day 1. If there was no immunogenicity assessment done pre-vaccination, the assessment post-vaccination on Day 1 can be used as the baseline value for the immunogenicity analysis, if available.

The results of the safety analysis will be presented by phase. Immunogenicity results will be presented per scheduled time point as appropriate. Listings will be shown per phase and time point.

Study day or relative day is defined as follows:

- Study Day = visit date – date of Day 1 + 1; if visit date  $\geq$  date of Day 1 (date of vaccination).
- Study Day = visit date – date of Day 1; if visit date  $<$  date of Day 1 (date of vaccination).

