### **5.3.3. Handling of Missing and/or Unquantifiable Immune Response Data**

Missing immune response data will not be imputed.

Values below the lower limit of quantification (LLOQ) will be imputed based on the type of analysis:

- Values below LLOQ will be imputed to LLOQ/2, except for the calculation of the geometric mean of the increase from baseline, values below LLOQ will be imputed to LLOQ.
- Data above the ULOQ will be imputed with the ULOQ.

The ULOQ and LLOQ values per assay will be available in the database.

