## **6.2. Appendix 2 Changes to Protocol-Planned Analyses**

No changes to planned analysis.

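### The deciding non-inferiority comparison ignores the baseline pre-F ELISA titer planned for every participant; the interval is valid, but precision that needs no new data is given up.

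*SAP*

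**What the plan says.** SAP 5.3.2 takes the interval that is compared with 0.67 (2/3) from an ANOVA of log-transformed titers, "with Day 15 pre-F ELISA titers as dependent variable and group as independent variable". Protocol 9.4.3.1 and the synopsis specify the same model. Baseline enters the between-group comparison only in a supporting role: "As a sensitivity analysis to assess the impact of baseline titers, the primary endpoint will also be evaluated adjusting for the respective baseline titers". A second sensitivity analysis uses Welch's ANOVA to allow unequal variances.

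The covariate is planned for everyone. Protocol 4.1 states: "Blood will be collected from all participants to assess humoral immune responses pre-vaccination, at 14 days post-vaccination". The Schedule of Activities places the Day 1 sample before vaccination.

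Protocol 9.2 sizes the trial for the unadjusted comparison, using the Day 15 standard deviation with no credit for baseline: "A total of 105 evaluable participants per group are needed to have 90% power to demonstrate non-inferiority". Neither document gives a correlation between baseline and Day 15 titers, or a reason for leaving baseline out of the deciding model.

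The SAP defines baseline in two ways. Section 5.3.2 says: "For immunogenicity, baseline is considered as the last assessment pre-vaccination". Section 5.1.1 adds that, if there is no pre-vaccination assessment, "the assessment post-vaccination on Day 1 can be used as the baseline value for the immunogenicity analysis". On missing values, SAP 5.3.3 says: "Missing immune response data will not be imputed".

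**The concern.** If baseline and Day 15 log titers are correlated, part of the Day 15 variance is predictable before vaccination. A group-only model leaves that part in the error term, so the interval is wider than the planned data require. Phase 3 material that is truly comparable then misses the 2/3 limit somewhat more often than it needs to.

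Two features make this worth raising. First, the planned power assumes a true GMR of exactly 1. If the new material is slightly lower but still well inside the margin, power falls quickly, and that is where extra precision helps most. Second, randomization uses permuted blocks and names no stratification factor (Protocol 6.3), so a chance difference in mean baseline titer carries straight into the unadjusted GMR. If the two planned analyses disagree, the less precise one decides, and the documents do not say how a disagreement would be read.

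**Working it through.** **Inputs.** From Protocol 9.2: log2 SD 1.3, true GMR 1, limit 2/3, 2-sided alpha 5% (one-sided 2.5%), 105 evaluable per group, about 120 enrolled per group. Assumptions not in the documents: the baseline to Day 15 correlation r on the log2 scale, shown as a range, and true GMRs of 0.95 and 0.90 as alternatives to the planning value.

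**1. The plan's own figure.** The distance from GMR 1 to the limit is log2(1.5) = 0.585. The standard error is 1.3 × √(2/105) = 0.179. The noncentrality is 0.585/0.179 = 3.26. With 208 degrees of freedom, noncentral-t power is 90.1%, and 105 is the smallest group size that reaches 90%. The stated figure reproduces. With the limit read literally as 0.67, power at 105 is 89.4%. The allowance also fits: 105/(1 − 0.125) = 120.

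**2. Power after adjustment.** The residual SD is 1.3 × √(1 − r²) and the degrees of freedom are 2n − 3.

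| Setting | Unadjusted | r = 0.1 | r = 0.2 | r = 0.3 | r = 0.5 | r = 0.7 |
|---|---|---|---|---|---|---|
| 105 per group, GMR 1 | 90.1% | 90.3% | 91.2% | 92.5% | 96.3% | 99.5% |
| 105 per group, GMR 0.90 | 67.1% | 67.5% | 68.8% | 71.2% | 79.2% | 92.0% |
| 120 per group, GMR 1 | 93.5% | – | 94.3% | 95.3% | 98.0% | – |

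At GMR 0.95 and 105 per group, power is 80.9% unadjusted against 84.4% (r = 0.3) or 90.5% (r = 0.5). Allowing for random baseline imbalance lowers the adjusted figures by at most about 0.3 points. With that allowance, r = 0 gives 89.9% against 90.1% unadjusted.

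**3. What the interval looks like at 105 per group.** The half-width on the log2 scale is t × residual SD × √(2/105), and the smallest observed GMR that passes is (2/3) × 2^(half-width).

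| | Unadjusted | r = 0.2 | r = 0.3 | r = 0.5 |
|---|---|---|---|---|
| Half-width (log2) | 0.354 | 0.347 | 0.337 | 0.306 |
| Smallest passing GMR | 0.852 | 0.848 | 0.842 | 0.824 |

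**4. Chance imbalance.** A difference in mean baseline of one standard error multiplies the unadjusted GMR by 2^(r × 1.3 × √(2/105)). That is a shift of 2.5%, 3.8% or 6.4% at r = 0.2, 0.3 or 0.5.

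**5. Error rate and disagreement, by simulation at 105 per group.** At a true GMR of 2/3 and r = 0.5 (40,000 trials), 2.4% of trials pass unadjusted and 2.5% adjusted, so the change does not loosen the test. At GMR 1 and r = 0.5, 6.4% of trials pass only when adjusted and 0.6% only when unadjusted. At low correlation the exchange is nearly even: about 0.8% against 0.7% at r = 0.1, and 1.9% against 0.9% at r = 0.2.

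**The case against.** The best reply is that nothing is broken. The group-only ANOVA is valid and is specified consistently in the protocol, synopsis and SAP. It meets its stated power, and the adjusted result will be reported anyway. All of that stands, and it is why this is a recommended improvement and not a correction.

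The benefit also rests on a correlation that the documents do not give. At r of 0.2 or below and GMR 1, the gain is about 1 point or less, and the striking figures need r of 0.5 or more. The gains at GMR 0.90 add a second assumption that is not the planning case; Protocol 4.2 says the groups differ only in lots, at identical dose. If losses fall short of 12.5%, unadjusted power moves towards 93.5% and less is left to gain (0.8 point at r = 0.2, 1.8 at r = 0.3). These limits stand too, but they do not reverse the balance. The worst case is a loss of about 0.1 to 0.2 point at r = 0, against gains of 2 to 6 points at r = 0.3 to 0.5.

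Finally, the two baseline definitions cannot affect the current primary interval, which uses no baseline value. That is correct. They do affect the planned adjusted sensitivity analysis and the fold increases, and they would have to be settled before baseline could enter the deciding model.

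**Conclusion.** The point holds. The deciding interval is valid and adequately powered under the plan's assumptions, but it sets aside a covariate planned for every participant and an adjusted model already written into the SAP. With 105 evaluable per group, SD 1.3 and GMR 1, the power given up is about 1 point at r = 0.2, 2.4 at r = 0.3 and 6.2 at r = 0.5. It is larger if the true GMR is below 1. The size depends wholly on r, which the documents do not report, so confidence in the magnitude is moderate. Confidence in the direction is high: adjustment leaves the type I error unchanged and costs almost nothing if baseline proves uninformative. The change is worth making, but the trial is not invalid without it.

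**What to change.** Before unblinding:

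- In SAP 5.3.2, make the primary model an ANCOVA of log2 Day 15 pre-F ELISA titer on group and log2 baseline pre-F ELISA titer. Take the GMR and its 2-sided 95% interval from the adjusted group difference and compare it with the same limit.
- Keep the group-only ANOVA and Welch's ANOVA as sensitivity analyses.
- Define the covariate as the last pre-vaccination value and reconcile SAP 5.1.1 with 5.3.2, so that a post-vaccination Day 1 sample is never used as the covariate. State which of the two below-LLOQ rules in SAP 5.3.3 applies to it.
- Add an exception to SAP 5.3.3 for the covariate only: set a missing baseline to the mean log2 baseline pooled over both groups, so that no participant with a Day 15 titer is dropped. Day 15 titers stay unimputed.
- Amend Protocol 9.4.3.1 and the synopsis to match, and replace the entry "No changes to planned analysis" in SAP Appendix 2 with a record of the change.

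The cost is a formal protocol amendment (Protocol 10.3.1) and an SAP update. No new samples, participants or assays are needed, since two planned analyses change places. If the sponsor's earlier studies show r of 0.2 or below, the return is only about 1 point of power at GMR 1, and the sponsor can weigh that against the amendment.

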### **5.3.3. Handling of Missing and/or Unquantifiable Immune Response Data**

Missing immune response data will not be imputed.

Values below the lower limit of quantification (LLOQ) will be imputed based on the type of analysis:

- Values below LLOQ will be imputed to LLOQ/2, except for the calculation of the geometric mean of the increase from baseline, values below LLOQ will be imputed to LLOQ.
- Data above the ULOQ will be imputed with the ULOQ.

The ULOQ and LLOQ values per assay will be available in the database.

## **5.4. Secondary Endpoint**

### **5.4.1. Definition of Endpoint(s)**

The secondary endpoint is RSV virus neutralization antibody (VNA A2) titers at 14 days after vaccination.

### **5.4.2. Analysis Methods**

VNA A2 titers will be analyzed descriptively. Descriptive statistics of the actual values (geometric mean and 95% CI) will be calculated at all timepoints. Additionally, geometric mean fold increases from baseline and corresponding 95% CIs will be calculated, as well as the percentage of participants with 2- and 4- fold increases from baseline.

Graphical representations will be created as applicable.

Geometric mean fold rises (GMT Phase3 CTM/GMT Phase 2b CTM) might also be calculated in a similar manner as for pre-F ELISA.

### **5.4.3. Handling of Missing and/or Unquantifiable Immune Response Data**

Missing immune response data will not be imputed.

Values below the lower limit of quantification (LLOQ) will be imputed as described in Section 5.3.3.

## **5.5. Safety Analyses**

Safety endpoints (secondary endpoints):

- Solicited local (injection site) and systemic AEs for 7 days after vaccination
- Unsolicited AEs for 28 days after vaccination
- SAEs and AESIs until 6 months after vaccination

Safety analyses will be performed on the FAS. Continuous variables will be summarized using the following statistics, as appropriate: number of observations, median, minimum and maximum. Frequencies and percentages (one decimal place) will be generated for categorical variables. No formal comparisons between groups will be provided.

Safety data will be analyzed by study intervention regimens as designed per protocol, per phase and also across the entire study period where applicable. For unsolicited AE, denominator for the percentages is the number of participants in the considered population and phase for a certain regimen (incidence per 100 participants/phase). For solicited AEs, the denominator for the percentages is the number of participants with data assessed by the investigator in the considered population and phase for a certain regimen (incidence per 100 participants/phase).

### **5.5.1. Adverse Events**

#### **5.5.1.1. Definitions**

Solicited AEs shown in the tables are extracted from the investigator assessment pages (CE) of the CRF. For unsolicited AEs, only the AEs within the 28-day period following vaccination will be presented in the safety tables except for SAE and potential AESI cases, which will be captured and tabulated in the outputs covering the whole study period. Unsolicited non-serious adverse events collected outside the 28-day period following the vaccination will be presented through listings.

For AESI analyses, the following subcategories are defined:

- Potential AESIs as identified by the investigator
- Potential AESIs selected programmatically

Those include all reported AEs that are identified by the selection rule:

- SMQ (Standardised MedDRA Queries) = “EMBOLIC AND THROMBOTIC EVENTS (SMQ)”  
or
- (SUB\_SMQ1 = “HAEMATOPOIETIC THROMBOCYTOPENIA (SMQ)” and SCOPE in (“BROAD”, “NARROW“)) or HLT (higher level term)=“Thrombocytopenias”

- Potential AESIs qualified for assessment

Potential AESIs (programmed/CRF) that have risk levels assessed by one of the following three criteria are considered 'qualified for assessment':

- Brighton Collaboration Level (Level 1-5)
- CDC Tier (non-tier 1/ 2, tier 1, tier 2)
- PRAC criteria (confirmed, possible, probable, unlikely, criteria not met)

Solicited administration site symptoms by definition will be considered as related to the study vaccine.

The severity of the AEs will be classified as grade 1 to 4. Solicited events of grade 0, not reported in the CE domain, will therefore not be reported in the AE analysis.

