## SAFETY EVALUATIONS

Safety assessments will include the monitoring of AEs and vital signs.

AEs and special reporting situations, whether serious or non-serious, that are related to study procedures or that are related to non-investigational sponsor products will be reported from the time a signed and dated informed consent form (ICF) is obtained until the end of the study/early withdrawal. Solicited AEs, collected through a participant diary, will be recorded from the time of vaccination until 7 days post-vaccination. All other unsolicited AEs and special reporting situations, whether serious or non-serious, will be reported from the time of vaccination until 28 days post-vaccination. All SAEs, AESIs, and AEs leading to discontinuation from the study (regardless of the causal relationship) are to be reported from the moment of vaccination until completion of the participant's last study-related procedure, which may include contact for safety follow-up. All AEs will be followed until resolution or until clinically stable.

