### **8.3.1. Time Period and Frequency for Collecting AE, SAE, and AESI Information**

#### **All AEs**

AEs and special reporting situations, whether serious or non-serious, that are related to study procedures or that are related to non-investigational sponsor products will be reported from the time a signed and dated ICF is obtained until the end of the study/early withdrawal.

Clinically relevant medical events not meeting the above criteria and occurring between signing of ICF and moment of vaccination will be collected on the Medical History eCRF page as pre-existing conditions.

Solicited AEs, collected through a participant diary, will be recorded from the time of vaccination until 7 days post-vaccination.

All other unsolicited AEs and special reporting situations, whether serious or non-serious, will be reported from the time of vaccination until 28 days post-vaccination.

All SAEs and AEs leading to discontinuation from the study (regardless of the causal relationship) are to be reported from the moment of vaccination until completion of the participant's last study-related procedure, which may include contact for safety follow-up. The sponsor will evaluate any safety information that is spontaneously reported by an investigator beyond the time frame specified in the protocol.

See Section [7.2](#) for procedures associated with withdrawal of consent.

All AEs will be followed until resolution or until clinically stable.

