#### **5.5.1.2. Analysis of Adverse Events**

Number and percentage of participants with at least one particular AE (unsolicited/solicited) will be tabulated. Unsolicited AEs will be summarized by System Organ Class and Preferred Term.

Solicited AEs will be summarized by class (administration site, systemic) and preferred term. AESI analyses will be summarized by Interest Category and Preferred Term.

For solicited AEs, the following tables will be provided: summary, by worst severity grade, at least grade 3, related (systemic only), time to onset (in days) and duration (in days). Note: Duration is defined as number of days from the start of the event until resolution of the event. The time to first onset is defined as (date of first onset – reference date + 1). The reference date is the start date of the post-dose period.

For unsolicited AEs following tables will be provided: summary table (including SAE, fatal outcome, potential AESI, AE leading to study discontinuation), all events, most frequent, at least grade 3, related, AE leading to study discontinuation, SAE, related SAE, potential AESIs qualified for assessment and potential AESI.

Moreover, table with Covid-19 related AEs, potential AESI as identified by the investigator, potential AESIs selected programmatically and potential AESI qualified for assessment will be created.

Potential AESIs selected programmatically will be tabulated by categories: '*Embolic and thrombotic events (SMQ)*' and '*Haematopoietic Thrombocytopenias (SMQ) (broad) or HLT = Thrombocytopenias*'. Potential AESI determined programmatically, related to study vaccine (investigator assessment), will be tabulated similarly.

Potential AESIs as identified by the investigator, will be tabulated by categories: '*Embolic and thrombotic events (SMQ)*' and '*Haematopoietic Thrombocytopenias (SMQ) (broad) or HLT = Thrombocytopenias*', and '*Other*'. Potential AESI as identified by the investigator, related to study vaccine (investigator assessment), will be tabulated similarly.

Potential AESIs qualified for assessment will be tabulated by categories: '*Embolic and thrombotic events (SMQ)*' and '*Haematopoietic Thrombocytopenia (SMQ) (broad) or HLT=Thrombocytopenias*'.

All AESI analyses will be presented by phase as well as by time interval. The definition of the different time intervals can be found in Section [5.1.2](#).

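### The SAP's table of AEs leading to study discontinuation omits late non-serious events that the protocol collects, and can mix two time windows

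*SAP*

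**What the plan says.** **Collection.** Protocol 8.3.1 states: "All SAEs and AEs leading to discontinuation from the study (regardless of the causal relationship) are to be reported from the moment of vaccination". The period closes with the participant's final study procedure. The synopsis (Safety Evaluations) has the same rule, with AESIs added. Neither passage sets a seriousness condition. The shorter window applies to the remainder: "All other unsolicited AEs and special reporting situations, whether serious or non-serious, will be reported from the time of vaccination until 28 days post-vaccination".

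**Analysis scope in the protocol.** Protocol 9.4.4 includes AEs with onset up to 28 days after vaccination, plus all SAEs and AESIs. For AEs with later onset it allows separate summaries, listings or both, as an option.

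**Tabulation in the SAP.** SAP 5.5.1.1 sets the limit as follows: "only the AEs within the 28-day period following vaccination will be presented in the safety tables except for SAE and potential AESI cases". The two exempt categories are tabulated over the whole study. For what remains, the section says: "Unsolicited non-serious adverse events collected outside the 28-day period following the vaccination will be presented through listings".

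**Planned outputs.** SAP 5.5.1.2 gives the unsolicited-AE summary table a row for AEs leading to study discontinuation. Its list of separate tables includes "all events, most frequent, at least grade 3, related, AE leading to study discontinuation, SAE, related SAE". No time window is attached to the discontinuation table or row.

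**The concern.** The protocol puts AEs leading to study discontinuation with SAEs for collection, so a late one is recorded on purpose. The SAP's exception to the 28-day limit names SAEs and potential AESIs but not this category, although the SAP plans a table for it. Whether a late event of this kind is counted then depends on its seriousness or AESI status, not on whether it ended participation.

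Two consequences follow. The table and summary row can combine late serious events from the whole study with non-serious events from the first 28 days only. They can also disagree with the disposition summary: SAP 5.2 counts study discontinuations and reasons for termination throughout the study, and protocol 7.2 allows an AE as a withdrawal reason at any time.

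What is at stake is the completeness and internal consistency of one descriptive safety count.

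**Working it through.** The plan states no figure to reproduce. The check compares rules and then sizes the gap in calendar time.

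**Step 1: follow three events through the rules.** Each starts on Day 60 and leads to study discontinuation.

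| Event | Collected (protocol 8.3.1) | Enters the tables (SAP 5.5.1.1) | Other presentation |
|---|---|---|---|
| SAE | yes | yes, exempt from the limit | listing and/or narrative |
| Non-serious potential AESI | yes | yes, exempt from the limit | listing and/or narrative |
| Non-serious, not a potential AESI | yes | no | listing; narrative as appropriate |

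Only the third row is affected. The first two can be counted in the discontinuation table; the third cannot.

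**Step 2: look for wording that overrides the limit.** SAP 5.5 says that safety data are analysed by phase and, where applicable, over the entire study. That is a general statement. The rule in 5.5.1.1 is specific to unsolicited AEs and names its exceptions, so it governs.

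**Step 3: size the gap, in days after vaccination.**

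Inputs:
- Vaccination is Day 1 (SAP 5.1.1), so the last visit on Day 183 is vaccination + 182. Its window is ±14 days (protocol, Visit Windows), giving 182 − 14 = 168 to 182 + 14 = 196.
- The table limit is 28 days. If the tables follow the post-dose period in SAP Table 3, the limit is the later of 28 days and the 28-day visit. With that visit's ±5-day window, it can reach 28 + 5 = 33.

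Formula: share outside the table = (last visit − limit) / last visit.

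| Last visit | Limit 28 days | Limit 33 days |
|---|---|---|
| 168 | 140/168 = 83.3% | 135/168 = 80.4% |
| 182 | 154/182 = 84.6% | 149/182 = 81.9% |
| 196 | 168/196 = 85.7% | 163/196 = 83.2% |

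The central value is 84.6%, with a range of 80.4% to 85.7%.

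**Step 4: weight of one event.** With 120 participants per group, one uncounted participant is 1/120 = 0.8 percentage points of an arm. The documents give no rate for late non-serious AEs leading to discontinuation, so an expected number cannot be computed.

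**The case against.** The strongest reply is that the SAP does what the protocol's analysis section asks. Protocol 9.4.4 has the same scope as SAP 5.5.1.1, and the safety endpoints match it: unsolicited AEs for 28 days, SAEs and AESIs to 6 months. AEs leading to discontinuation are not an endpoint of their own, and a longer collection window does not oblige the sponsor to tabulate over it. All of this stands. A reader might infer that the SAP departs from the protocol's planned analysis; the documents do not support that. The mismatch is between the collection rule and a table that the SAP itself plans.

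A second reply is that nothing is lost. This also stands. Late non-serious AEs are listed, SAP 5.5.1.2 provides listings and/or narratives as appropriate for participants who leave because of an AE, and the disposition summary gives whole-study counts by reason. But a listing does not complete a count and percentage in a table.

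A third reply is that titles and footnotes belong to the data presentation specifications, which are a separate document and may state the window. That is possible. A label would remove the risk of misreading, but would not make the count complete.

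Finally, the 84.6% could be misread as the share of events missed. It is calendar time only. The affected event must be non-serious, not a potential AESI, start after the window and still end participation, in a single-dose study whose only scheduled contact after the 28-day call is one telephone call at 6 months.

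**Conclusion.** The point holds as a minor inconsistency. The table and summary row for AEs leading to study discontinuation would omit late non-serious events that are not potential AESIs, although the protocol collects them for the whole study, and could include late SAEs. For the omitted type, about 85% of follow-up time (80% to 86%) lies outside the table.

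It would go too far to say that the table covers only the first 28 days, or that all later non-serious AEs are excluded: SAEs and potential AESIs, serious or not, are exempt from the limit.

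The verdict assumes that the specific rule in SAP 5.5.1.1 governs the discontinuation table, and that the unseen data presentation specifications do not widen it. The number of events is probably very small; that is a judgement from the single-dose design, not a figure in the documents. Safety is descriptive, so no endpoint, hypothesis test or primary conclusion is affected.

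**What to change.** In SAP 5.5.1.1, extend the exception to read: *except for SAEs, potential AESIs and AEs leading to study discontinuation, which are tabulated for the whole study period*. Apply it to both the separate table and the summary row in 5.5.1.2. If the sponsor prefers the 28-day limit, the minimum is to state the window of that table and row and refer to the listing, though the count then stays incomplete.

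The cost is one phrase and slight extra programming. The data are already collected, and protocol 9.4.4 already permits summaries of later AEs, so no protocol amendment is needed. The reported count may become slightly less favourable.
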